16.0 DATA SAFETY AND MONITORING BOARDS

All trials initiated by the Brown University Oncology Research Group (BrUOG) are subject to oversight by the Data Safety Monitoring Board (DSMB). This board meets two times per year with any additional meetings scheduled when needed. The responsibilities are as follows:

- Familiarize themselves with the research protocol (s)
- The DSMB reviews trial performance information such as accrual information.
- Review interim analyses of outcome data and cumulative toxicity data summaries to determine whether the trial should continue as originally designed, should be changed, or should be terminated based on these data.
- The DSMB also determines whether and to whom outcome results should be released prior to the reporting of study results.
- All adverse events are reviewed by the committee, with assurances that these have been in fact sent for review to all pertinent IRBs.
- Review of reports of related studies to determine whether the monitored study needs to be changed or terminated.
- Review major proposed modifications to the study prior to their implementation (e.g., termination, dropping an arm based on toxicity results or other reported trial outcomes, increasing target sample size).
- Following each DSMB meeting, provide the study leadership with written information concerning findings for the trial as a whole related to cumulative toxicities observed and any relevant recommendations related to continuing, changing, or terminating the trial.

The study leadership will provide information on cumulative toxicities and relevant recommendations to the local principal investigators to be shared with their IRB's.

17.0 STATISTICS

SAMPLE SIZE AND STATISTICAL DESIGN

Three patients will be accrued to level 1. If no dose limiting toxicities are observed following completion

7/21/16, 7/26/16, 8/1/16, 8/2/16, 8/3/16, 8/4/16, 8/9/16, 8/15/16, 8/16/16, 8/17/16 submitted Merrimack, 10/3/16 Merrimack edits, 10/7/16. 32
Re-submitted Merrimack 10/11/16, 11/15/16 from Merrimack, 11/17/16, 11/30/16 back to Merrimack, approved Merrimack 1/5/17,
1/26/17, 2/7/17 company review, 2/8/17, 2/13/17, 3/2/17 company, 3/3/17, approved company 3/23/17, RN/Pharmacy/EXEC review
3/31/17, 3/31/17 BrUOG, to company 4/6/17, Ipsen 4/18/17, BrUOG 4/20/17, Ipsen approved 5-4-17, FDA 5-5-17, FDA IND exemption
5/18/17, Protocol change 5/18/17, Protocol change 7/10/17 with IB v10, 8/17/17, Amendment # 1 4/6/18, Amendment #2 8/14/18,
Amendment # 3 12/8/18

of 4 weeks of treatment (2 cycles) then accrual to dose level 2 will proceed. If a DLT is observed in one of the first 3 patients in a dose level, then accrual for that level will be expanded to 6 patients. Accrual will continue in this way until the MTD is determined. Two or more instances of DLT in a cohort of 6 patients will result in the preceding dose level being defined as the MTD. After determination of the MTD, the final cohort will be expanded so that a total of 25 patients are treated on study. The final cohort will be treated at the MTD.

If a patient is unable to receive 4 weeks of treatment (2 cycles) for reasons other than a dose limiting toxicity, they will be replaced in a cohort. Patients who require a treatment delay of more than 8 weeks not due to toxicity will be removed from protocol treatment.

If two or more instances of DLT in a cohort of 6 patients occurs in dose level 1 then dose level -1 of nanoliposomal irinotecan will be investigated.

Definition of Dose Limiting Toxicities

- Grade 4 neutropenia (ANC < 500/mm³)
- ANC <1000/mm³ with fever (temp > 101) or infection
- Grade 4 thrombocytopenia: Platelets <25,000/mm³
- Platelets <50,000/mm³ requiring transfusion
- Grade 3 or 4 treatment related non-hematologic toxicities excluding alopecia.
 - Grade 3 nausea, vomiting or diarrhea will only be considered a dose limiting toxicity if it occurs for greater than 72 hours despite maximal medical support.
 - Grade 3 electrolyte abnormalities will not be considered dose limiting toxicities if the electrolyte disorder can be corrected to grade 2 or less within 72 hours.
 - A grade 4 electrolyte abnormality will be considered a DLT.

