APPENDIX SECTION:

APPENDIX A INFORMED CONSENT

APPENDIX B ELIGIBILITY CHECKLIST

APPENDIX C COMMON TOXICITY CRITERIA

APPENDIX D ECOG PERFORMANCE STATUS

APPENDIX E CASE REPORT FORMS

1.0 OBJECTIVE

1.1 Primary Objective

1.1.1. To evaluate the maximum tolerated dose of nanoliposomal irinotecan with continuous low-dose temozolomide for patients with recurrent glioblastoma.

1.1.2 To assess the preliminary response rate and progression free survival of nanoliposomal irinotecan with continuous low-dose temozolomide in patients with recurrent glioblastoma.

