Nanoliposomal irinotecan will be administered by IV infusion over approximately 90 minutes. One cycle is 14 days, subsequent doses should be administered on the first day of each cycle +/- 3 days. An additional 1 day is provided for a holiday.

Three patients will be accrued to level 1. If no dose limiting toxicities are observed following completion of 4 weeks (2 cycles) of treatment then accrual to dose level 2 will proceed (patients must be evaluated prior to their cycle 3 treatment and this will be used to confirm DLTs). If a DLT is observed in one of the first 3 patients in a dose level, then accrual for that level will be expanded to 6 patients. Accrual will continue in this way until the MTD of nanoliposomal irinotecan with temozolomide 50mg/m²/day is determined. Two or more instances of DLT in a cohort of 6 patients will result in the preceding dose level being defined as the MTD. If two or more instances of DLT in a cohort of 6 patients occurs in dose level 1 then dose level -1 of nanoliposomal irinotecan will be investigated. After determination of the MTD, the final cohort will be expanded so that a total of 25 patients are treated on study. The final cohort will be treated at the MTD.

If a patient is unable to receive 4 weeks of treatment (2 cycles) for reasons other than dose limiting toxicity, they will be replaced in a cohort.

Premedication

All patients must be premedicated prior to nanoliposomal irinotecan infusion with standard doses of dexamethasone and a 5-HT3 antagonist or other anti-emetics as per standard institutional practices for irinotecan administration. Atropine may be prescribed prophylactically for patients who experienced acute cholinergic symptoms in previous cycles.

Premedication prior to temozolomide is not required and may be administered as per institutional standard of care.

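### A level cleared at 0 of 3 can be declared the MTD on those 3 patients, without facing the protocol's own two-of-six test, and no written rule lets expansion DLTs revise the declaration

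*Combined protocol and SAP*

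**What the plan says.** The first primary objective (section 1.1) is "To evaluate the maximum tolerated dose of nanoliposomal irinotecan with continuous low-dose temozolomide for patients with recurrent glioblastoma".

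The escalation scheme appears in sections 4.0 and 17.0 in the same form:

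- Start: "Three patients will be accrued to level 1".
- Moving up: "If no dose limiting toxicities are observed following completion of 4 weeks (2 cycles) of treatment then accrual to dose level 2 will proceed".
- The only trigger for taking a level to six during escalation: "If a DLT is observed in one of the first 3 patients in a dose level".
- Setting the MTD: "Two or more instances of DLT in a cohort of 6 patients will result in the preceding dose level being defined as the MTD".
- Expansion: "After determination of the MTD, the final cohort will be expanded so that a total of 25 patients are treated on study". That cohort is treated at the MTD.

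Neither section sets a minimum number of patients at the preceding level before it is named.

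After the declaration, three things bear on toxicity. Sections 5.2 and 5.3 define DLTs over each patient's first 28 days and attach individual dose reductions. Section 16.0 provides a data safety monitoring board (DSMB) that reviews cumulative toxicity and may change or end the trial; on frequency it says "This board meets two times per year with any additional meetings scheduled when needed". Section 15.6 allows early closure for unacceptable risk. None of these gives a number. The one numerical rule in the expansion, in section 17.0, concerns response: stop if 0 or 1 of the first 13 evaluable patients at the MTD respond.

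**The concern.** The test that the protocol uses to reject a dose is two or more DLTs in 6. A level that shows 0 of 3 skips it on the way up. If the next level then fails, the skipped level is named the MTD by default, because "will result in the preceding dose level being defined as the MTD" carries no condition on how many patients that level has had. The declaration is complete before any expansion patient is treated.

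At stake is the answer to the first primary objective. The expansion will produce DLT data on the declared dose, but the plan does not say whether those data can change or qualify the declaration. If they turn out unfavourable, the team would have to improvise a rule after seeing them.

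**Working it through.** **Inputs.** Cohorts of 3 and 6, the two-of-six rule and the total of 25 are from sections 4.0 and 17.0; the 28-day DLT window is from section 5.2. The plan states no target or expected DLT rate, so the true rate p is assumed over 10% to 50%. I also assume that 2 or 3 DLTs in the first 3 patients stop a level, which the text does not state.

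**Stated figure.** The plan gives no operating characteristic for the escalation, so there is none to reproduce. Its alpha of 0.098 belongs to the response test and does not bear on this point.

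**Step 1: the path.** Level 1 at 0/3, then level 2 with two or more DLTs in 6: level 1 is the MTD on 3 patients. The same holds for level 2 if level 3 fails.

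**Step 2: clearing a single level.**

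- As written: (1−p)³ + 3p(1−p)²·(1−p)³.
- With six required: (1−p)⁶ + 6p(1−p)⁵.
- The difference is the chance of 0/3 followed by two or more DLTs in the next 3: (1−p)³ × P(≥2 of 3).

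At p = 0.4: as written 0.216 + 0.093 = 0.309; with six 0.047 + 0.187 = 0.233; difference 0.216 × 0.352 = 0.076.

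| True DLT rate (assumed) | P(0/3) | Cleared as written | Cleared with six | Difference | Fails two-of-six, given 0/3 |
|---|---|---|---|---|---|
| 20% | 0.512 | 0.709 | 0.655 | 0.053 | 0.104 |
| 30% | 0.343 | 0.494 | 0.420 | 0.074 | 0.216 |
| 40% | 0.216 | 0.309 | 0.233 | 0.076 | 0.352 |
| 50% | 0.125 | 0.172 | 0.109 | 0.063 | 0.500 |

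**Step 3: how usual the path is.** The share of clearances resting on 0/3 is P(0/3) divided by the as-written column, for example 0.216/0.309 = 0.70 at 40%. It lies between 69% and 81% for p from 10% to 50%.

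Chaining the three levels gives the share of MTDs set at level 1 or 2 by the preceding-level rule that rest on 3 patients. For assumed rates 0.20/0.40/0.50:

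- level 1 on 3 patients: 0.512 × (1 − 0.309) = 0.354
- level 1 on 6: 0.197 × 0.691 = 0.136
- level 2 on 3: 0.709 × 0.216 × (1 − 0.172) = 0.127
- level 2 on 6: 0.709 × 0.093 × 0.828 = 0.055
- share: (0.354 + 0.127)/0.672 = 0.72

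Over five such assumed profiles the share runs from 71% to 79%.

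**Step 4: what 3 patients can show.** The one-sided 95% exact upper limit on the DLT rate is 1 − 0.05^(1/3) = 63% after 0/3, against 39% after 0/6 and 58% after 1/6.

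**Step 5: how many follow.** The fewest patients used before such a declaration is 3 + 3 = 6 (level 2 stopped within its first 3), leaving 25 − 6 = 19. The most is 6 + 3 + 6 = 15, leaving 10. So 10 to 19 more are treated at that dose, 13 to 22 in all, ignoring replacements and an early futility stop.

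**The case against.** The strongest reply is that this is one accepted variant of the 3+3 scheme against another, and that the expansion makes good the small cohort. Safety is a stated objective (section 1.2), the board can call extra meetings, sites notify the coordinating office of serious events within 24 hours (section 11.6), and the trial can be closed for unacceptable risk. The gain from a six-patient check is also modest: at a true rate of 20% it rejects about 5 more levels per 100, and at 40% about 8 more, before requiring that the next level also fails.

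Much of this stands, and it rules out several stronger readings that a reader might infer:

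- *The whole primary dose conclusion rests on 3 patients.* Only the formal declaration does; 13 to 22 patients would be treated at that dose by the end.
- *The MTD level never faces the two-of-six test.* A level with 1 DLT in its first 3 does face it. At a 40% rate that route supplies 0.093/0.309, or 30%, of clearances.
- *Expansion DLTs will be ignored.* The documents do not say so. They are collected, acted on for the individual and reviewed by the board. What is missing is a rule linking them to the MTD.
- *Oversight is limited to two meetings a year.* Section 16.0 allows additional ones.
- *Level 3 cleared at 0/3 becomes the MTD.* The text is silent on a cleared top level, so this would be inference.

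The reply does not remove the gap. The safeguards are discretionary and carry no number, and none of them determines the MTD.

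**Conclusion.** The point holds in this form. Followed exactly, the plan can declare level 1 or 2 the MTD on 3 patients with no DLT, and under the assumed profiles that is the usual way such a declaration arises. No written rule then lets the DLTs of the next 10 to 19 patients confirm or revise it.

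The size is moderate. Requiring six lowers the chance that a single level is cleared by 5 to 8 percentage points at true rates of 20% to 50%. The loss at 20% is the price of the check, and the reductions at 40% and 50% are its benefit. All rates are assumed, and none of these figures is the probability that the wrong dose is named. The trial can run without the change, but the change should be made: it applies the plan's own criterion to the dose that the plan will report and expand.

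**What to change.** In sections 4.0 and 17.0:

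1. Call a level cleared on 3 patients a provisional MTD until six DLT-evaluable patients there have been assessed under the existing two-of-six criterion. The first three expansion patients complete the six.
2. State that a failed check returns the decision to the existing preceding-level rule.
3. Report the final MTD with the DLT count and confidence interval from all patients treated at that level.

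No dose and no new toxicity threshold is proposed.

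**Cost if the check passes:** wording, one pause of about 4 weeks (the 28-day window) after the third expansion patient, and no added patients.

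**Cost if it fails:** a further pause and fewer patients at the final MTD. For example, 0/3 at level 1, 0/3 at level 2 and a failed level 3 with 6 patients uses 12; three more at level 2 makes 15. If level 2 then fails, 25 − 15 = 10 remain, giving 3 + 10 = 13 at level 1. That is exactly the first-stage number for response, with no slack for replacements or inevaluable patients. If level 1 also fails on three more, 25 − 18 = 7 remain for level -1, fewer than 13. The amendment should say whether the total of 25 may then be exceeded.

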APPENDIX B: Checklist

Onivyde (nanoliposomal irinotecan) and Metronomic Temozolomide for Patients With Recurrent Glioblastoma: A Phase IB/IIA Brown University Oncology Research Group Study

Inclusion Criteria

(y/n) Histologically confirmed glioblastoma multiforme or gliosarcoma

(y/n) Progression after at least one line of therapy.

(y/n) Patient must have received temozolomide and radiation but it is not required that they were given concurrently.

(y/n) Voluntary, informed consent, Date signed _____

(y/n) Age \geq 18

(y/n) All males and women of childbearing potential, must be willing to consent to use an adequate barrier birth control measure while on treatment and for at least 2 months after the last treatment on study

(y/n) Brain MRI completed with contrast

(y/n) Patient must be able to tolerate brain MRI with contrast

(y/n) EKG within 8 weeks study entry

(y/n) Life expectancy >12 weeks as noted by treating investigator

(y/n) Absolute neutrophil count $\geq 1,500/\mu\text{L}$, Date _____

(y/n) Platelet $\geq 100,000/\mu\text{L}$, Date _____

(y/n) Total bilirubin $\leq 1.0 \times \text{ULN}$, Date _____

(y/n) AST $\leq 2.5 \times \text{ULN}$ and ALT $\leq 2.5 \times \text{ULN}$ Institution

(y/n) Creatinine $\leq 1.5 \times \text{ULN}$

(y/n) HGB $\geq 9.0\text{g/dL}$

(y/n) Albumin levels $\geq 3.0 \text{ g/dL}$

(y/n) Karnofsky performance score ≥ 60

(y/n) Recovered (\leq grade 1) from the effects of any prior surgery, radiotherapy or other anti-neoplastic therapy, except alopecia. See section 3.1.10

(y/n) Stable corticosteroid dose at least 7 days prior to day 1

 (y/n) Patients must have assessable (measurable) disease at baseline by brain MRI. Must be contrast enhancing. The tumor size will be measured in millimeters and is the largest cross-sectional area using perpendicular measurements of contrast enhancing abnormality.

Exclusion Criteria:

 (y/n) Non-GBM primary invasive malignant neoplasm that is considered by treating investigator to likely cause death in the next 5 years.

 (y/n) Patient not to be receiving any cancer therapy or investigational anti-cancer drug.

 (y/n) Radiation therapy or cytotoxic chemotherapy or biologics or immunotherapy within previous three weeks from day 1 of drug (no anticancer treatment of any kind within 3 weeks of day 1 of drug).

 (y/n) Evidence of an active infection requiring intravenous antibiotic therapy

 (y/n) Women of child bearing potential without a negative serum pregnancy test (minimum sensitivity 25 IU/L or equivalent units of HCG) within 7 days prior to Day 1 of treatment. Post-menopausal women (surgical menopause or lack of menses \geq 12 months) do not need to have a pregnancy test, please document status.

 (y/n) pregnant or breastfeeding

 (y/n) Unwillingness or inability to follow the procedures required in the protocol, site to have documentation to confirm at time of registration.

 (y/n) Patient with a history of Gilbert's disease or known UGT1A1*28 allele. (Assessment for the UGT1A1*28 allele is not required for protocol entry.)

 (y/n) Myocardial infarction, unstable angina pectoris, stroke within 6 months of study registration.

 (y/n) NYHA Class III or IV congestive heart failure

 (y/n) Known hypersensitivity to any of the components of nanoliposomal irinotecan , other liposomal products, or temozolomide

 (y/n) Investigational anticancer therapy administered within 4 weeks. See section 3.2.13

 (y/n) Any medical condition that in the opinion of the Investigator may interfere with a subject's participation in or compliance with the study. Must receive confirmation in writing from treating MD.

 (y/n) Live vaccines within 30 days prior to the first dose of trial treatment and while participating in the trial. See section 3.2.14

 (y/n) Use of CYP3A4 enzyme-inducing anticonvulsants phenytoin and strong CYP3A4 inducers is not allowed. Conmed log to show patients has been off any of these exclusionary products for \geq 2 weeks from day 1.

The support documentation, per the requirements under the study parameters section of this study, as well as the consent form and this checklist, must be faxed to the BrUOG Central Office at the time of registration. Please check if "Enclosed", state reason when "Not Enclosed," or check if "Not Applicable."

1) Eligibility Form Enclosed Not Enclosed Not Applicable

2) Heme/Onc initial note Enclosed Not Enclosed Not Applicable

3) Pathology Report(s) Enclosed Not Enclosed Not Applicable

4) MRI/CT Report(s) Enclosed Not Enclosed Not Applicable

5) Lab Source Document Enclosed Not Enclosed Not Applicable

6) ICF signature page

7) Other documents, please list _____

IRB approval date of protocol: _____

Hospital where patient will be treated with Oncologist: _____

Date patient will begin treatment: _____ Primary Physician (Oncologist):_____

Your signature: _____

APPENDIX C

NCI CTC Version 4

Toxicity will be scored using NCI CTC Version 4 for toxicity and adverse event reporting. A copy of the NCI CTC Version 4 can be downloaded from the CTEP homepage: (<http://ctep.info.nih.gov>). All appropriate treatment areas have access to a copy of the CTC Version 4

APPENDIX D

ECOG PATIENT PERFORMANCE STATUS

STATUS	KARNOFSKY	ZUBROD-ECOG- WHO	Description
No complaints	100	0	Normal activity
Able to carry on normal activities	90	1	Symptoms, but fully ambulatory
Normal activity with effort	80		
Cares for self. Unable to carry on normal activity or to do active work	70	2	Symptomatic, but in bed <50% of the day
Requires occasional assistance, but able to care for most of his needs	60		
Requires considerable assistance and frequent medical care	50	3	Needs to be in bed >50% of the day, but not bedridden
Disabled, requires special care and assistance	40		

Severely disabled. Hospitalization indicated though death non imminent	30	4	Unable to get out of bed
Very sick. Hospitalization Necessary. Active support treatment necessary	20		
Moribund	10		
Dead	0		

From: Minna J.D., Higgins G.A and Glapstein E.J. Cancer of the lung: In: DeVita V, Hellman S., Rosenberg S., (Eds.). Cancer: Principles and Practice of Oncology, Lippincott, Philadelphia, 1984, p. 536

APPENDIX E

CASE REPORT FORMS

Attached separately are the BrUOG Case Report Forms

7/21/16, 7/26/16, 8/1/16, 8/2/16, 8/3/16, 8/4/16, 8/9/16, 8/15/16, 8/16/16, 8/17/16 submitted Merrimack, 10/3/16 Merrimack edits, 10/7/16. 54
Re-submitted Merrimack 10/11/16, 11/15/16 from Merrimack, 11/17/16, 11/30/16 back to Merrimack, approved Merrimack 1/5/17,
1/26/17, 2/7/17 company review, 2/8/17, 2/13/17, 3/2/17 company, 3/3/17, approved company 3/23/17, RN/Pharmacy/EXEC review
3/31/17, 3/31/17 BrUOG, to company 4/6/17, Ipsen 4/18/17, BrUOG 4/20/17, Ipsen approved 5-4-17, FDA 5-5-17, FDA IND exemption
5/18/17, Protocol change 5/18/17, Protocol change 7/10/17 with IB v10, 8/17/17, Amendment # 1 4/6/18, Amendment #2 8/14/18,
Amendment # 3 12/8/18
